**A Prospective Randomized Clinical Trial Evaluating Surgical Conditions during
Laparoscopic Bariatric Surgery with Deep *versus* Moderate Neuromuscular
Blockade**

PI: [name], MS¹
Professor

Co-PI: [name], MD¹
Resident

Co-I [name]
Associate Professor

[name]
Associate Professor

Co-I: [name], MD²
Associate Professor
Director, Missouri Bariatric Services

Statistician: [name].
Research Assistant Professor³

¹Department of Anesthesiology and Perioperative Medicine

²Department of General Surgery, Division of Bariatric Surgery

³Department of Health Management and Informatics, Office of Medical Research
University of Missouri
Columbia, Missouri 65212

Version 1: January 5, 2016
IRB project number: 2004620

Contact Information: [name], MS
Department of Anesthesiology and Perioperative Medicine
University of Missouri-Columbia

[name]

[name]

[contact]

[contact]

Email: [contact]

2.1 Objectives:

This prospective, randomized, single-blind trial will randomize patients undergoing laparoscopic bariatric surgery to either deep (0 twitches, 1-2 PTC) or moderate (reappearance of T2) neuromuscular blockade (NMB). Within each NMB group, patients the initial insufflation pressure will be either 10 or 15 mm Hg:

Primary Endpoint:

1. Surgeon initial satisfaction with operating conditions

Secondary Endpoints:

1. Percentage of procedures that can be performed at low (10 mm Hg) versus high (15 mm Hg) insufflation pressures at each level of NMB
2. Percentage of procedures requiring additional NMB and/or insufflation pressures to achieve satisfactory intraoperative surgical conditions
3. Quantification of postoperative pain medication requirements with deep versus moderate NMB

2.1.1 Clinical Hypotheses:

Primary Hypothesis:

We hypothesize that deep neuromuscular block (NMB)

1. provides better intra-operative surgical conditions than moderate NMB during laparoscopic bariatric surgery

Exploratory Hypotheses:

We hypothesize that deep neuromuscular block (NMB):

1. allows the use of lower insufflation pressures during laparoscopic bariatric surgery
2. decreases postoperative pain and the need for postoperative pain medication

2.2 Background & Rationale:

Obesity affects more than 78 million adults in the United States and it is estimated that 35% of the US population is obese (body mass index ≥ 30) with the highest incidence (40%) in women aged 40 to 59 years.¹ Obese individuals have increased comorbidity including an increased risk for coronary heart disease, hypertension, dyslipidemia, type 2 diabetes, and sleep apnea. The treatment of obesity and its related comorbidities costs nearly \$150 billion annually and this cost is expected to increase if obesity is not stemmed.² Dieting has proven to be only marginally effective in the treatment of obesity, but surgery results in substantial long-term weight loss.³ As a result, more than 179,000 bariatric procedures are performed in the US each year with the majority of these surgeries using laparoscopic techniques.⁴

Neuromuscular blockade (NMB) is routinely used during laparoscopic surgery to optimize both intubating and operating conditions for the anesthesiologist and the surgeon, respectively. Recent research has shown that in laparoscopic abdominal procedures, deep NMB is associated with superior operating conditions.⁵⁻⁸ However, maintaining deep NMB can be a challenge to anesthesiologists concerned about rapid emergence and the risk of postoperative residual paralysis. It is, therefore, obvious that surgeons and anesthesia providers have conflicting goals for the level of muscle relaxation that should be maintained during many surgical procedures.

The introduction of sugammadex (Bridion[®], Merck Sharp & Dohme Corp., Oss, The Netherlands), a new neuromuscular reversal agent with the ability to rapidly reverse deep rocuronium-induced NMB, will finally provide the anesthesia provider the opportunity to maintain deep neuromuscular relaxation throughout the entire surgery without compromising time to emergence and increasing post-operative complications.⁹ However, sugammadex will undoubtedly cost much more than neostigmine, the anticholinesterase inhibitor presently used to reverse NMB, and hospital pharmacies will

have to be convinced that the benefit of improved operating conditions is worth the additional cost associated with the use of sugammadex.

[figure not shown]
Recently, there has also been interest in maintaining low insufflation pressure during laparoscopic surgery because lower pressures may decrease postoperative pain.¹⁰ It is hypothesized that deep NMB will provide good surgical conditions and minimize postoperative pain at low insufflation pressures of 7 to 10 mmHg, but this theory has not been adequately evaluated, especially in obese patients.

At the present time, there is no conclusive evidence that surgeons need deep NMB for laparoscopic bariatric surgery and even that surgeons can discriminate between moderate and deep NMB.¹¹ The goal of this prospective, randomized, assessor-blinded controlled trial is to test the hypothesis that deep NMB provides optimal surgical conditions during laparoscopic bariatric surgery in the morbidly obese patient. In addition, we will determine if deep NMB allows the surgeon to utilize lower insufflation pressure and decreases postoperative pain requirements after laparoscopic bariatric surgery.

2.3 Study Design:

Study design: prospective, randomized, assessor-blinded controlled trial that will be performed at a single academic hospital. The surgeons, subjects, and individuals performing the postoperative assessments will be blinded to the study group assignment. The anesthesia providers responsible for the clinical care of the patients will be aware of the rocuronium NMB treatment group and NMB and insufflation status throughout the surgical procedure.

2.4 Study Design:

2.5 Study Procedures:

- I. Patient population: this study will enroll 145 adults undergoing elective laparoscopic bariatric surgery. Our aim is to randomize 140 patients and this will allow 5 subjects to drop out of the study after enrollment.
- II. Inclusion criteria:
 - a. Age \geq 18 years
 - b. ASA I-III
 - c. BMI \geq 35
- III. Exclusion criteria:
 - a. Inability to obtain written informed consent
 - b. Pregnancy or breastfeeding
 - c. Allergy to rocuronium, sugammadex, or any anesthetic agents used in the protocol
 - d. Known or suspected neuromuscular disorders
 - e. Significant renal disease with a serum creatinine \geq 2 mg/dl
 - f. Significant liver disease
 - g. A family history of malignant hyperthermia
- IV. Randomization: On the day of surgery, patients will be randomized to one of four groups: 1. moderate NMB + 10 mm insufflation pressure (IP); 2. moderate NMB + 15 mm IP; 3. deep NMB + 10 mm IP; or 4. deep NMB + 15 mm IP. Randomization will be stratified for the four groups so that obese patients with BMI of 35 to 45 and those with a BMI $>$ 45 are equally distributed between the groups.
- V. Blinding: The surgeon, operating room staff, patients, personnel in the postanesthesia care unit (PACU) as well as the investigators collecting the postoperative data will be blinded to the group allocation. The surgeon will also

be blinded to the initial insufflation pressure. The rocuronium infusions will be prepared in a room away from any of the blinded personnel. The anesthesia providers administering the anesthesia will be aware of the randomization and the dose of rocuronium that the patient is receiving. The TOF watch will be draped so that the surgeons and operating room personnel are unable to observe it during the procedure. The insufflation pressures will also be covered. .

VI. Anesthetic management

a. Monitoring

1. All patients will be monitored with standard monitors including ECG, non-invasive blood pressure, pulse oximetry, esophageal temperature, capnography, and a BIS® depth of anesthesia monitor.
2. Muscle relaxant monitoring – neuromuscular function will be monitored using acceleromyography with the TOF-Watch® SX (Organon Ireland Ltd, a subsidiary of Merck and Co., Inc., Swords, Co. Dublin, Ireland). The TOF tracing will be stabilized after induction of anesthesia (prior to the administration of muscle relaxant drugs) according to the manufacturer's recommended protocol.

b. Anesthetic Technique – all patients will receive a standardized general anesthetic technique and all anesthetic medications (with the exception of sugammadex) will be dosed on the ideal body weight rather than actual weight.

1. Premedication – midazolam, 1-2 mg iv in the holding area
2. Preoxygenation with 100% oxygen for a minimum of 3 minutes
3. Induction – propofol, 2 – 2.5 mg/kg, iv and fentanyl, 2-3 micrograms/kg, iv. Additional propofol or fentanyl may be administered at the discretion of the anesthesia provider
4. Intubation – succinylcholine, 1.5 mg/kg, iv after loss of consciousness to facilitate tracheal intubation

5. Maintenance – ventilation with air/oxygen to achieve a $\text{FiO}_2 = 0.6$ and inhaled desflurane adjusted to maintain a BIS® level of 40-60, and fentanyl, 25-50 micrograms iv as needed determined by the anesthesia provider. The FiO_2 of oxygen can also be increased if determined necessary by the anesthesia provider.
6. Maintenance of muscle relaxation – after return of neuromuscular function (return of twitches) after intubation with succinylcholine, patients will be dosed in accordance with their randomization assignment to achieve either moderate or deep NMB during surgery.

c. The rocuronium dosing protocol during the maintenance phase of anesthesia will be:

1. Moderate NMB group [1-3 twitches in the train of four (TOF)] – rocuronium, 0.2 mg/kg iv, followed by a rocuronium infusion which will be started at the appearance of 1 twitch and adjusted to maintain 1-3 twitches throughout the procedure
2. Deep NMB group [0-1 posttetanic count (PTC)] – rocuronium, 0.6 mg/kg iv, followed by a rocuronium infusion at 10 mcg/kg/min. The infusion will be adjusted to maintain 0-1 PTC throughout the procedure.

d. Reversal of NMJ blockade - The rocuronium infusions will be continued until the fascia is closed. At that point, the rocuronium infusions will be discontinued. The level of NMJ block will be assessed with the TOF watch and the patients will be reversed with sugammadex (using actual body weight) after assessment of the TOF ratio. Reversal will be dosed as follows:

1. Deep block (defined as a TOF count of 0 with recovery of 1-2 post-tetanic counts) will be reversed with sugammadex, 4 mg/kg, iv
2. Moderate block (defined as the reappearance of T_2 in the TOF) will be reversed with sugammadex, 2 mg/kg iv

- e. Extubation: Prior to extubation, patients will be following verbal commands (opening eyes, head lift) and will also manifest a sustained tetanic response to ulnar nerve stimulation using a standard neuromuscular stimulator. The information in combination with the clinical judgement of the anesthesia provider will be used to determine the time of extubation. The TOF ratio will not be used to determine when to extubate the patient but the TOF ratio at the time of extubation will be recorded.

VII. Postoperative Pain Management

- a. Acetaminophen, 1000 mg iv, will be given during the maintenance phase and repeated every 6 hours for the first 24 hours after surgery.
- b. Fentanyl PCA will be started in the postanesthesia recovery room and continued for the first 24 – 48 hours after surgery.

VIII. Perioperative assessments

- a. Surgeon satisfaction – the primary endpoint is the surgeon's satisfaction with the level of NMB during surgery at the start of the case (the initial score). The satisfaction level will be rated with a five-point ordinal scale ranging from 1 (extremely poor) to 5 (optimal conditions). This scale is outlined in detail in table 1 (page 15) and is adopted from a previously published studies.⁶ For each patient, the first surgeon satisfaction rating during the procedure (prior to any rescue measure) will be the primary outcome measure.
- b. During the laparoscopic procedure, the surgeon will score the surgical working conditions. The first rating will occur when the NMB level is stable at either deep or moderate block (per randomization) and the intra-abdominal pressure is either 10 or 15 mm Hg per a second randomization list. The surgeon will be blinded to the insufflation pressure at this point. If the conditions are rated as extremely poor or poor (surgical rating of 1-2, Table 1), the following steps will be taken in an incremental manner. The surgeon may also request rescue

treatment if the surgical rating scale is 3 (acceptable), but he anticipates deterioration in the surgical condition during the procedure :

1. Increase the insufflation pressure to a maximum of 15 mm Hg –the surgeon will reassess the surgical field after the intra-abdominal pressure is stable at 15 mm Hg for 2-3 minutes. At this point the insufflation pressure will remain at 15 mm Hg for the remainder of the procedure.
2. Additional muscle relaxation – if the surgeon rates the working conditions as 1 (extremely poor) or 2 (poor) after increasing the insufflation pressure to 15 mm Hg, the surgeon may then request additional muscle relaxant. At this point the anesthesia provider will check the level of NMB. If the patient is in the moderate group and has 1 or more twitches, the anesthesia provider will administer a bolus dose of rocuronium, 0.3 mg/kg iv. If the patient has only 0-1 PTC, the anesthesia provider will administer an equal volume of iv saline. The surgeon will rate the surgical working conditions at 2-3 minutes after the additional dose of medication.

- c. Intra-abdominal insufflation pressures and TOF ratio measurements will be recorded every 15 minutes during the procedure.
- d. Surgeons will be asked to rate their satisfaction with the surgical field every 30 minutes during the procedure.
- e. Perioperative variables will also be recorded including the duration of surgery, time from administration of NMJ reversal (sugammadex) to extubation, time from end of surgery to exit from the OR, time in the PACU, and length of hospital stay.
- f. Postoperative verbal pain levels (0 = no pain to 10 = worst imaginable pain) and opioid requirements will be assessed daily. Patients will also be asked about the presence or absence of shoulder pain.

- g. Postoperative variables including the need for postoperative mechanical ventilation, re-intubation, residual paralysis, pneumonia, infections, and other adverse events during the hospital stay. The need for ICU admission and length of hospital stay will also be collected.

2.6 Study Duration:

The Missouri Bariatric Service at the University of Missouri-Columbia performs over 600 bariatric procedures per year. The Director for this service, [name] [name], is a co-investigator on the study. He has 3 full day operating blocks per week and we estimate that we can easily enroll 15 patients per month.

We estimate that patient enrollment can be completed in 9 months. We will need an additional 3 months after enrollment is complete for data analysis and abstract/manuscript preparation.

Statistical Analysis and Sample Size Justification:

[figure not shown]
Data analysis will be based on an intent-to-treat approach. The primary endpoint will be the first surgeon satisfaction rating measured on a five-point ordinal scale (Table 1). The experimental layout is a randomized two-factor design so the primary analysis will be the two-way Analysis of Variance (ANOVA) with interaction. A statistically significant interaction will be followed by pairwise comparisons to identify and estimate treatment combination differences. The standard ANOVA assumes a normally distributed outcomes with homogeneous variances and so the robustness of the results will be checked against an aligned-rank test for the two-way layout.¹²

Secondary outcomes will be time to extubation or discharge, and total pain medication requirements. The same two-way analysis as described for surgeon satisfaction will be used for each of these endpoints. Residuals will be examined and need for a modest transformation or rank-based methods considered. Moderate and deep NMB will also be compared with respect to the proportion of cases randomized to low insufflation pressure that were completed at low pressure. The chi-square test of proportions will be used for that analysis.

Sample size – Sample size estimates are based surgeon satisfaction rating as this is the primary outcome. Figure 3 of Martini et al.⁶ gives the frequency distribution of the surgeon satisfaction score under moderate and deep block. Scores for the moderate block have the greatest variability and so for sample size purpose the proportions from Fig. 3 were used to estimate the standard deviation of the surgeon satisfaction score ($\sigma = 1.1$). Based on literature and clinical judgement we powered the study to have at least 80% power to detect statistically significant ($p < 0.05$) effects for the main effects and interaction term in a two-way analysis of variance assuming the following configuration of mean satisfaction scores and a common standard deviation of 1.1.

		Pressure	
		10mmHG	15mmHG
Block	Moderate	2.5	4.0
	Deep	4.3	4.8

Power curves for each of the ANOVA effects are displayed in Figure 1. The required minimum sample size is 108 subjects, allocated 27 per treatment combination. To guard against potential optimism in these calculations (actual variances could be larger or effects smaller) we intend to recruit 35 subject per treatment combination for a total sample size of 140.

Power calculations were carried out using GLMPOWER procedure in SAS v 9.3.

Specific Drug Supply Requirements:

The anesthetic agents utilized in this study (including rocuronium) are routinely used for this type of surgery and are acceptable patient costs. However, sugammadex just received FDA approval in December 2015 and is not currently used for NMB reversal at our institution. We will receive adequate supplies of sugammadex from Merck &Co. so that there will be no charge to the patients for this medication.

2.11 References:

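### Preoperative opioid users are eligible, no recording of prior use is specified, and the planned model for total pain medication has no term for it, so this secondary comparison may give up some precision

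*Combined protocol and SAP*

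**What the plan says.** The third secondary endpoint in section 2.1 is "Quantification of postoperative pain medication requirements with deep versus moderate NMB". Section 2.1.1 adds an exploratory hypothesis that deep block reduces postoperative pain and the need for pain medication. The statistical section states: "Secondary outcomes will be time to extubation or discharge, and total pain medication requirements". It applies to them the same two-way ANOVA (block, pressure, interaction) as to surgeon satisfaction, with residual checks and a possible transformation or rank-based method. It names no covariate.

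On who enters, section 2.5, item I says that "this study will enroll 145 adults undergoing elective laparoscopic bariatric surgery". Inclusion a-c covers age, ASA class and BMI. Exclusions a-g cover consent, pregnancy or breastfeeding, drug allergy, neuromuscular disorder, renal disease, liver disease and family history of malignant hyperthermia. Opioid use and chronic pain are not mentioned. Item IV stratifies randomization on BMI only.

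On data, item VIII lists assessments from surgery onwards. After surgery, pain levels and "opioid requirements will be assessed daily". No preoperative opioid item is specified anywhere. All patients receive a fentanyl PCA (item VII.b).

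**The concern.** Patients who already take opioids may need more opioid after surgery whatever block they receive. If so, prior use adds between-patient variance to the total, and an ANOVA without a term for it leaves that variance in the error. A transformation or rank method deals with the shape of the distribution, but does not remove a difference that existed before randomization.

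At stake is the precision of one secondary comparison. The sample size was set on surgeon satisfaction, and no SD, effect size or power is given for pain medication, so the plan does not show that precision is adequate there. A covariate prespecified now is uncontroversial; one added after the data are seen would be open to challenge.

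**Working it through.** **The plan's own figure.** There is none for this endpoint. The only calculation is for surgeon satisfaction: "at least 80% power to detect statistically significant" effects, "assuming the following configuration of mean satisfaction scores" and "a common standard deviation of 1.1", with the result "The required minimum sample size is 108 subjects, allocated 27 per treatment combination". From the tabulated means, the block effect is 4.55 − 3.25 = 1.3, the pressure effect 4.4 − 3.4 = 1.0, and the interaction contrast (4.3 − 2.5) − (4.8 − 4.0) = 1.0. With SD 1.1 and 27 per cell, noncentral-F power is above 99.9% for block, 99.7% for pressure and 64.8% for interaction. The stated 108 therefore does not reproduce for the interaction, which needs 39 per cell (156). That is a separate matter and has no bearing on the opioid endpoint.

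**Inputs from the plan.** 35 per cell, so 70 deep versus 70 moderate; residual df 140 − 4 = 136; test level 0.05.

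**Assumptions, none in the documents.** Log total opioid has SD s among non-users (0.5, 0.8 or 1.0). A proportion p of patients are prior users (5%, 10%, 20%), needing m times as much (1.5, 2, 3). Deep block truly reduces the total by 20%, an effect of ln 0.8 = −0.223. A yes/no covariate removes all the variance due to prior use.

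**Formulas.**
- Added variance: v = p(1 − p)(ln m)².
- Noncentrality: λ = (ln 0.8)² / (2σ²/70), with σ² = s² if adjusted and σ² = s² + v if not.
- Power: probability that a noncentral F(1, 136, λ) exceeds the 5% critical value.

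**Middle case at s = 0.5.** v = 0.10 × 0.90 × (0.693)² = 0.0432, which is 0.0432/0.25 = 17% of the residual variance. Adjusted, λ = 0.0498/0.00714 = 6.97 and power is 74.6%. Unadjusted, λ = 6.97/1.173 = 5.94 and power is 67.7%. Matching the adjusted precision without the covariate would take 140 × 1.173 ≈ 164 patients.

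**Across the assumptions** (power unadjusted, with the loss in percentage points):

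| Log SD | Adjusted power | 5% users, 1.5 times | 10% users, 2 times | 20% users, 3 times |
|---|---|---|---|---|
| 0.5 | 74.6% | 73.3% (1.3) | 67.7% (6.8) | 50.4% (24.2) |
| 0.8 | 37.4% | 37.0% (0.4) | 35.4% (2.0) | 30.1% (7.4) |
| 1.0 | 25.9% | 25.7% (0.2) | 25.0% (0.9) | 22.4% (3.4) |

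The SD matters because the relative increase in variance is v/s²: the same v of 0.0432 is 17% of the variance at SD 0.5, 6.8% at 0.8 and 4.3% at 1.0.

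**Cross-check on another scale.** With 15% users and a shift of 1 within-group SD, v = 0.15 × 0.85 = 0.1275 and R² = 0.1275/1.1275 = 0.113. Adjustment cuts the standard error by 1 − √(1 − 0.113) = 5.8%, takes a comparison with 80% power to 84.5%, and is worth an unadjusted N of 140/(1 − 0.113) ≈ 158. Over 5-30% users and shifts of 0.5-1.5 SD, the cut runs from 0.6% to about 18%.

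**Cost in degrees of freedom.** Power at SD 0.5 is 74.59% with 136 or 135 residual df.

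**The case against.** The case against is that nothing here is an error. Unadjusted ANOVA of a randomized factorial is valid, the endpoint is secondary, and even BMI, the stratification factor, is not in the stated model. Choosing prior opioid use is a matter of judgement, and every figure for its effect is assumed. All of this stands, and it limits the point to an optional improvement.

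Five stronger readings are tempting but unsupported:

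- A reader might infer that prior use will not be recorded. The protocol has no baseline data list. BMI and creatinine must be known for stratification and exclusion, yet neither appears in item VIII. Absence from that list shows only that recording is not specified; the clinical record may hold the information.
- A reader might infer that a prior user's total mostly reflects tolerance. The documents say nothing on this. Under the assumed multipliers, the share due to prior use is one third at 1.5 times and one half at 2 times, and exceeds half only above that.
- A reader might treat chance imbalance as a further harm. At 10% users, the 95% range of the between-arm difference is ±1.96 × √(0.10 × 0.90 × 2/70) = ±9.9 percentage points, and 0.099 × ln 2 = 0.069 is about 31% of the assumed effect. The unadjusted standard error already includes this variation, so it is the same loss counted again, and it is not bias.
- A reader might take the 24-point loss as typical. It needs 20% users, 3 times and SD 0.5 together.
- A reader might extend the point to pain scores. The statistical section applies the two-way analysis to time to extubation or discharge and to total pain medication; it states no such analysis of pain scores.

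**Conclusion.** The point holds as a possible loss of precision in the secondary comparison of total pain medication. The plan admits prior opioid users, specifies no recording of that use, and fits no term for it. Systematic bias is not at issue, and the primary endpoint is unaffected.

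The size cannot be derived from the documents. Under the stated assumptions it runs from negligible, where prior use is rare or weakly predictive or the other variation is large, to material, where use is common, strongly predictive and the other variation is small. Confidence in any single figure is low. The reason to act is that the remedy is cheap.

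**What to change.** Record daily preoperative opioid use (yes/no) from the preoperative history before randomization. In the statistical section, prespecify it as a covariate in the two-way model for total pain medication, on the transformed scale if a transformation is used. If a rank-based method is used, apply it to covariate-adjusted residuals, or report the adjusted model alongside.

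The cost is one baseline field, one residual degree of freedom and a sentence on the rank-based case. If prior use proves rare or weakly predictive, the gain will be negligible. Eligibility, sample size, randomization and the primary analysis do not change.

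### Operation type is not a listed variable, a stratum or a model term, so the two-way analyses may be less precise than they could be, though they remain valid

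*Combined protocol and SAP*

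**What the plan says.** **Eligibility.** Under 2.5 Study Procedures, item I, "this study will enroll 145 adults undergoing elective laparoscopic bariatric surgery". The inclusion and exclusion criteria (items II and III) cover age, ASA class, BMI, consent, pregnancy or breastfeeding, allergy, comorbidity and family history. None names or excludes an operation, and none separates first-time from revision surgery.

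**Randomisation.** Item IV stratifies so that "obese patients with BMI of 35 to 45 and those with a BMI $>$ 45 are equally distributed between the groups". No other stratum is given.

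**Data items.** Item VIII.e says "Perioperative variables will also be recorded including the duration of surgery" and continues with several recovery times and length of stay. Items VIII.f and VIII.g add pain, opioid use and complications. Operation type is not named in any of them.

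**Analysis.** In Statistical Analysis and Sample Size Justification, "the primary analysis will be the two-way Analysis of Variance (ANOVA) with interaction". For the secondary endpoints, "Secondary outcomes will be time to extubation or discharge, and total pain medication requirements", and "The same two-way analysis as described for surgeon satisfaction will be used for each of these endpoints". Completion at low pressure is compared between block groups without adjustment: "The chi-square test of proportions will be used for that analysis". No analysis contains a covariate, and the BMI class used in randomisation is absent too.

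**The concern.** The scheduled operation is fixed before randomisation and known from the booking. Different operations may need different working space, take different times and lead to different opioid use and stay. Lack of space in the operative field is itself part of the rating scale (Table 1, score 2). Where such differences exist, a model with only block and pressure puts them into the error term.

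The one operative descriptor that is listed, duration of surgery, cannot stand in for operation type. It is measured after randomisation and may itself be affected by block and pressure.

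What is at stake is precision. The interaction is the weakest of the three planned tests on the primary rating, and a significant result there triggers the pairwise comparisons. Pain medication and time to discharge have no power statement at all.

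**Working it through.** **Inputs from the sample-size section.** Mean ratings: moderate block 2.5 (10 mmHg) and 4.0 (15 mmHg); deep block 4.3 and 4.8. Common SD 1.1, significance level 0.05, stated minimum 27 per cell (108), planned 35 per cell (140).

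**Effects implied by these means**
- Block: (4.3 + 4.8)/2 − (2.5 + 4.0)/2 = 4.55 − 3.25 = 1.3
- Pressure: (4.0 + 4.8)/2 − (2.5 + 4.3)/2 = 4.4 − 3.4 = 1.0
- Interaction: (4.0 − 2.5) − (4.8 − 4.3) = 1.5 − 0.5 = 1.0

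**Power without a covariate.** I used the noncentral F distribution with 1 and 4n − 4 degrees of freedom, for n per cell. The noncentrality is effect² / (SD² × 2/(2n)) for a main effect and effect² / (4 × SD²/n) for the interaction. At n = 35 these are:
- Block: 1.69 / (1.21 × 2/70) = 48.9
- Pressure: 1.00 / (1.21 × 2/70) = 28.9
- Interaction: 1.00 / (4 × 1.21/35) = 7.23

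| n per cell | Block | Pressure | Interaction |
|---|---|---|---|
| 27 | >99.9% | 99.7% | 64.8% |
| 35 | >99.9% | >99.9% | 76.1% |

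The plan's minimum of 108 therefore does not reproduce for the interaction, which needs 39 per cell (156) for 80% power. That is a separate defect of the sample-size statement. It matters here only because it sets the baseline at 76.1%.

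**Power with the covariate.** The documents give no share of variance due to operation type, so the share R² is an assumption shown as a range. The error SD becomes 1.1 × √(1 − R²), one error degree of freedom is spent on a two-level factor, and the equivalent extra sample is 140/(1 − R²) − 140.

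| Assumed R² | Error SD | Interaction power, 35 per cell | Equivalent extra patients |
|---|---|---|---|
| 0 | 1.100 | 76.1% | 0 |
| 0.01 | 1.094 | 76.5% | 1 |
| 0.02 | 1.089 | 76.9% | 3 |
| 0.05 | 1.072 | 78.2% | 7 |
| 0.10 | 1.044 | 80.4% | 16 |
| 0.15 | 1.014 | 82.5% | 25 |

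Spending three error degrees of freedom instead of one leaves the R² = 0 figure at 76.1%.

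**Continuous secondary outcomes.** The main-effect difference detectable with 80% power at 70 versus 70 (normal approximation) is (1.96 + 0.84) × √(2/70) × √(1 − R²). This is 0.474 SD at R² = 0, 0.462 at 0.05, 0.449 at 0.10 and 0.437 at 0.15.

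**Chance imbalance.** Suppose 30% of patients have the less common operation (assumption). The 95% range for the difference in share between block groups is ±1.96 × √(2 × 0.3 × 0.7/70) = ±0.152. If the operations differ by 0.8 SD (assumption), the block contrast shifts by up to 0.152 × 0.8 = 0.12 SD. The standard error is √(2/70) = 0.169 SD, so the shift is about 0.7 standard errors. The same two assumptions imply a between-operation variance of 0.3 × 0.7 × 0.8² = 0.134 SD², a share of about 12 to 13%. The shift is thus another view of the variance in the table, taken at its 95% extreme. It is not an additional loss.

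**The case against.** The strongest reply is that leaving a prognostic covariate out of a randomised factorial analysis is a legitimate choice, and that the primary hypothesis does not need it. That hypothesis is that deep block gives better conditions than moderate block, which is the block main effect, and its power already exceeds 99.9%. This stands.

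The gain may also be smallest for the primary outcome. The rating analysed is the first one, taken at the start of the case before any rescue, when little of the operation-specific work has been done. A share near zero is credible there, and at 1 to 2% interaction power is only 76.5 to 76.9%. This stands as well, and it is why the range begins at zero.

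Four stronger readings are tempting, and the documents support none of them.
- *Operation type will not be recorded.* The list in item VIII.e is open-ended. It also omits BMI, which must be captured in order to stratify. The operation will be in the surgical record. All that can be said is that type is not listed.
- *Operation type is a known source of variation.* The documents say nothing on the mix of operations or on outcomes by type. Its influence is clinical judgement.
- *Chance imbalance biases the comparisons.* It does not. The unadjusted standard error already contains this variation, and the error rate holds.
- *Adjustment cures the interaction's power shortfall.* It reaches 80% only if the share is about 10% or more, which nothing in the documents establishes.

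The reply does not remove the case for prespecification. Retrieving type afterwards gives the operation performed unless the scheduled one was captured, and a covariate chosen after the data are seen is not a planned adjustment.

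**Conclusion.** The point holds as one of precision. Eligibility is open to any elective laparoscopic bariatric operation, while operation type is absent from the listed variables, the strata and the models. If several types are performed and type is prognostic, the planned analyses are valid but less efficient than they could be, chiefly for total pain medication, time to discharge and the interaction.

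On the plan's means and SD, with an assumed variance share of 0 to 15%, the most that adjustment would add to interaction power at 35 per cell is 6.4 percentage points (76.1% to 82.5%), and the least is nothing. Over the same range the detectable main-effect difference on a continuous secondary outcome falls from 0.474 to 0.437 SD. The conclusion on the primary block effect is not at risk.

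**What to change.** 1. Record the scheduled procedure type, and primary or revision status, before randomisation. Use the scheduled operation and not the one performed.
2. Prespecify scheduled type as a fixed covariate, alongside the BMI class used in randomisation, in the two-way models for total pain medication, time to discharge and the initial rating.
3. Keep the unadjusted two-way ANOVA and the aligned-rank test as sensitivity analyses. The aligned-rank test can stay in its two-way form without the covariate.
4. Do not adjust for duration of surgery.

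The cost is one field from the booking and one to three error degrees of freedom for operation type, plus one for BMI class, out of 136. Recruitment, treatment and the randomisation scheme do not change. There is no gain from the type term if only one type of operation is performed. The sample-size statement for the interaction still has to be corrected separately.
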